- Infants with other severe concurrent illnesses such as neurological, cardiovascular, pulmonary, metabolic, endocrine, and renal disorders that would interfere with the conduct and results of the study
- Any other clinical condition that is a contraindication to the use of corticosteroid (e.g., bowel perforation)
- Infants who have received the live attenuated rotavirus vaccine (e.g. Rotateq) within 5 days prior to proposed administration of study drug.

In the unlikely event that the diagnosis of biliary atresia is established during exploratory laparotomy, but the surgeon did not perform a portoenterostomy (as may occur in cases of advanced cirrhosis), the subject will not be eligible for this study.

4.E. Primary and Secondary Outcome Measures

- Primary outcome measure:
Percentage of subjects with serum total bilirubin $<$ 1.5 mg/dL and with native liver at 6 months after portoenterostomy.
- Secondary outcome measures:
All measurements will be made at 12 and 24 months of age (unless noted otherwise):
 1. Serum total bilirubin concentration (and also at 3 months after portoenterostomy)
 2. Survival with native liver at 24 months of age

3. Growth
 - a. Weight for age Z-score (in subjects without ascites)
 - b. Height for age Z score
4. Serum biomarkers of sufficiency of fat-soluble vitamins
 - a. Vitamin A: molar ratio of serum retinol/retinol binding protein
 - b. Vitamin D: serum level of 25-hydroxy vitamin D
 - c. Vitamin E: ratio of serum vitamin E/total lipids
 - d. Vitamin K: International Normalized Ratio (INR)
5. Presence of ascites
- Tertiary outcome measures:

All measurements will be made at 12 and 24 months of age:

 1. International Normalized Ratio (INR)
 2. Serum albumin concentration
 3. Pediatric End-Stage Liver Disease (PELD) score
 4. Platelet count
 5. Serum sodium concentration
 6. Serum bile acid concentrations
 7. Serum concentration of undercarboxylated prothrombin (PIVKA-II)
 8. Head circumference Z-score
 9. Mid-arm circumference and triceps skinfold thickness
 10. Health-related quality of life (HRQOL)
 11. Neurodevelopmental assessment (Bayley score)
 12. Immunologic response to routine childhood vaccination (at 18 months of age)

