Hypothesis 1b is that improved bile drainage, as determined by serum total bilirubin with native liver, will be improved in the infants treated with corticosteroids compared to those treated with placebo. Serum total bilirubin concentrations are measured at each clinical visit, including 3 and 6 months after portoenterostomy, and at 12, 18 and 24 months of age. (The time point of 6 months after portoenterostomy is the primary endpoint). A serum total bilirubin value >1.5 mg/dL, transplant or death, is indicative of failure of the portoenterostomy. The time to the first value >1.5 mg/dL (when the value is initially >1.5 and then declines to ≤ 1.5 , the time to the first value >1.5 mg/dL after the decline will be used), to transplant or to death will be considered time to failure of the procedure. The two groups will then be compared by a Cox regression model fitted to the time to failure. Since the test of the primary endpoint is a special case of this analysis, there is greater power for this comparison than for the primary endpoint.

Hypothesis 2 is that survival with native liver at 24 months of age is improved in infants treated with corticosteroids compared to those treated with placebo. In the 118 subjects in our survey of the ChiLDREN centers, 60 (51%) were transplanted by 24 months of age. Similar to the primary endpoint, we will have 80% power to show a 50% improvement in this measure (lowering the transplant rate from 50% to 25%).

Hypothesis 3 is that growth will be improved in infants treated with corticosteroids compared to those treated with placebo. These secondary endpoints, weight for age Z-score (in subjects without ascites) and height for age Z-score, are continuous. Children at the time of portoenterostomy are expected to have normal or near normal growth (mean Z-score near zero). Changes in weight and height Z-scores will be compared between treatment groups. For these endpoints there will be 80% power to identify a difference of 0.55 standard deviations (SD) between groups when 110 subjects are randomized. Since a mean Z-score of -1.0 or less would represent impaired growth and a mean > -0.5 would represent satisfactory growth, there will be almost 80% power to differentiate between these two outcomes.

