Prior to unmasking the study and the start of any formal analyses, the data for each variable will be examined to identify unusual values that need to be queried, patterns of missing values and whether their distributions are non-Gaussian (i.e., have significant skewness and kurtosis). These analyses are, in general, performed conditional on one or more covariates known to affect the variable being studied; for example, values may be examined conditioned on age of the infant or age at time of portoenterostomy. Data from variables with non-Gaussian distributions will be transformed, if necessary, before building statistical models. Missing data patterns will be examined and, when necessary for the data analysis, missing data may be imputed by appropriate methods depending on the pattern and mechanism of the missing data. Baseline variables will be compared between groups. If a baseline variable is identified as significantly different between groups and it may affect the outcome measure, the analysis of the outcome measure will be repeated with this baseline variable included as a covariate. All models will include clinical site as a random effect.

Aim 1: To determine whether corticosteroid therapy decreases serum bilirubin concentration after portoenterostomy.

Hypothesis 1a: The probability of an infant having good bile drainage at 6 month after portoenterostomy (as defined by a serum total bilirubin level <1.5 ml/dL) will be greater in subjects treated with corticosteroids than in those treated with placebo.

This is the primary hypothesis of this study, upon which the sample size was calculated. A generalized linear model (e.g., a logistic regression model) with random effects will be used to test this hypothesis. The dependent variable is dichotomous: whether the infant has good bile drainage or not; transplantation or death is considered a failure in all analyses. The covariates that will be included in the model are the treatment group, baseline total bilirubin level, age of the infant at portoenterostomy, complications before the surgery, gender and race of the infant, presence of major congenital anomalies, as well as site as a random effect. The test of the primary hypothesis is a test of whether the coefficient of treatment group is zero.

Hypothesis 1b: Improved bile drainage (as defined by a serum total bilirubin level <1.5 mg/dL) will remain for a longer period in infants treated with corticosteroids than in those treated with placebo.

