Using the same definition of good bile drainage as in the primary hypothesis, the duration of time with good bile drainage (time to onset of poor bile drainage, transplant or death, whichever comes first) will be modeled by Cox proportional hazards model using the same model as above. If there is a statistically significant difference, the profiles of the bilirubin for the two treatment groups will be compared and 95% confidence limits will be computed.

Aim 2: To determine whether corticosteroid treatment after portoenterostomy will improve outcome as defined by survival without transplantation at 24 months of age.

Hypothesis 2: Survival without liver transplantation will be greater at 24 months of age in infants treated with corticosteroids than in those treated with placebo.

A Cox proportional hazards model will be fitted to the time to transplant or death. The same covariates will be included in the model as for the previous hypothesis.

Aim 3: To determine whether corticosteroid treatment after portoenterostomy will improve growth of infants with biliary atresia.

Hypothesis 3: Weight and height Z-scores at 12 and 24 months of age will be higher in the infants treated with corticosteroids than in those treated with placebo.

The weight and height Z-scores at 12 and 24 months of age will each be modeled by a random effects model with the same covariates as above.

Aim 4: To determine whether corticosteroid treatment improves biochemical indicators of each of the fat-soluble vitamins after supplementation with standard doses.

Hypothesis 4a: Treatment with corticosteroids leads to improved bile drainage (hypothesis 1) which, in turn, increases the probability that an infant will achieve vitamin sufficiency of each of the fat-soluble vitamins following supplementation of AquADEK®.

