Each vitamin will be analyzed separately. For hypothesis 4a, each subject will be classified as having achieved or not achieved vitamin sufficiency, first with supplementation and then without supplementation. Vitamin sufficiency will be defined as having achieved the target concentration ranges specified in Section 4.N8. Although we can model the outcome as a function of treatment group, the underlying hypothesis is that the outcome is a function of bilirubin level. Therefore, we will model the outcome by logistic regression using bilirubin as a surrogate for bile drainage; bilirubin may be included in the model either as a continuous measure or as a dichotomy where <1.5 mg/dL is defined as good bile flow and ≥ 1.5 mg/dL as inadequate bile flow. Gender and race of the infant, presence of major congenital anomalies, as well as site as a random effect will be included as covariates.

Hypothesis 4b: Treatment with corticosteroids leads to improved bile drainage (hypothesis 1) which, in turn, reduces the dose required for supplementation and the length of time of supplementation for each of the fat-soluble vitamins.

As in hypothesis 4a, each vitamin will be analyzed separately. There are two components to this hypothesis. The first is the total amount of supplementation and the second is the length of supplementation. We will compute the total amount of supplementation up to 6 months of age as the first dependent variable and the time to achieving target concentrations without supplementation as the second dependent variable. The first variable (after transformation) will be analyzed by a random effects model with bilirubin as the independent variable and the same covariates as in hypothesis 4a. The second variable will be modeled by Cox regression with the same independent variable and covariates.

Aim 5: To determine whether corticosteroid treatment after portoenterostomy will decrease the incidence of persistent ascites or ascites that requires medical treatment.

Hypothesis 5: The incidence of ascites will be decreased at 12 and 24 months of age in infants treated with corticosteroids than in those treated with placebo.

Similar to hypothesis 2, a Cox proportional hazards model will be fitted to the time to diagnosis with ascites.

Other endpoints will be analyzed similarly depending on whether they are continuous, dichotomous or time-to-event.

5.C. Data Management

5.C1. Case Report Forms

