A common template for the informed consent form will be used at each clinical site with modifications in the format as necessary to meet the requirements of the respective institutional human subjects committees. The parents/guardians will retain a copy of the signed consent form; one copy will be retained for the subject's chart and one will be included in the research records. No collection of data related to the study or to procedures will be done prior to completion of the informed consenting process.

6.B4. Assent

Assent will not be sought from study subjects because they will be infants at entry into this study.

6.C. Potential Benefits

6.C1. Description of Possible Health Benefits to Subjects

The use of corticosteroid as an adjuvant therapy following portoenterostomy has the potential to increase bile drainage and decrease hepatobiliary inflammation in infants with biliary atresia. We do not know whether improved bile drainage 6 months after portoenterostomy will lead to better long-term outcome. However, the design of this clinical trial within ChiLDREN will allow us to generate data on long-term clinical outcome by: 1) assessing clinical outcome without liver transplantation at 2 years of age, and 2) continued follow-up up to 10 years through participation of the subject in the ChiLDREN prospective database study.

Study subjects will undergo formal developmental evaluation and their parents/guardians will assess the impact of chronic liver disease on HRQOL. These evaluations have not been previously done in children with biliary atresia, and have the potential to uncover opportunities for targeted therapeutic interventions to improve neurodevelopmental outcome and HRQOL to affected children and their families. These potential benefits will extend to all subjects, regardless of their randomization to treatment or placebo groups.

There is a potential benefit of monitoring for vaccine response and identification of the need for booster immunization.

If the trial demonstrates that corticosteroid therapy does not produce positive outcomes, the data may guide the medical community at large regarding the lack of efficacy of this approach, which should discourage the incorporation of corticosteroid therapy into routine clinical care.

6.C2. Description of any incentives or rewards offered for participation

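### The between-arm comparison of bilirubin profiles and its 95% confidence limits are planned only if the Hypothesis 1b Cox result is significant, although bilirubin concentration is an unconditional secondary outcome

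*Protocol*

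**What the plan says.** Aim 1 in section 5.B is worded in terms of concentration: "To determine whether corticosteroid therapy decreases serum bilirubin concentration after portoenterostomy". Section 4.E gives as the first secondary outcome "Serum total bilirubin concentration (and also at 3 months after portoenterostomy"), in a list otherwise measured at 12 and 24 months of age. No condition is attached.

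For Hypothesis 1b, section 5.B says that the time with good drainage (ended by poor drainage, transplant or death) "will be modeled by Cox proportional hazards model using the same model as above". That model is unconditional. The next sentence is not: "If there is a statistically significant difference, the profiles of the bilirubin for the two treatment groups will be compared". It continues that the profiles "will be compared and 95% confidence limits will be computed", so the limits fall under the same condition. By its position, the difference meant is the one tested by the 1b Cox model.

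Section 5.A2 describes 1b only as a time-to-failure analysis: "The two groups will then be compared by a Cox regression model fitted to the time to failure". Section 5.B ends with a general sentence: "Other endpoints will be analyzed similarly depending on whether they are continuous, dichotomous or time-to-event".

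**The concern.** The rule makes the production of an estimate depend on a p-value, and on the p-value of a different quantity. The 1b test concerns the time to crossing 1.5 mg/dL, transplant or death. Concentrations can differ between arms without that test reaching significance, and the reverse can also happen.

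Two things are at stake. After a non-significant 1b result, readers would have no promised between-arm estimate of concentration, and so no view of which differences remain compatible with the data. After a significant one, the profile difference is seen only in samples where a related statistic was large, which pushes the estimate away from zero on average.

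The treatment is also uneven. The analyses for Hypotheses 2, 3 and 5 carry no such condition, and this sentence is the only place in sections 5.A and 5.B that mentions confidence limits. This is a rule the protocol states, not a detail it leaves open.

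**Working it through.** **The plan's own figure.** Section 5.A.1 gives 110 subjects in total for 50% against 75%, two-sided 5%, 80% power. With unpooled variance:

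n per arm = (1.960 + 0.842)² × [0.50×0.50 + 0.75×0.25] / 0.25² = 7.849 × 0.4375 / 0.0625 = 54.94, total 109.9, so 110.

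The figure reproduces. It anchors 80% as the planned power of the primary test. Section 5.A2 says the 1b comparison has greater power than the primary, but gives no number, so 80% and 90% are taken as the planned region and lower powers as cases where the true effect falls short.

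**Chance that the comparison is not produced.** This equals 1 minus the power of the 1b test.

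| Power of the 1b test | Not produced |
|---|---|
| 5% (no effect) | 95% |
| 20% | 80% |
| 50% | 50% |
| 80% | 20% |
| 90% | 10% |

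**Inflation when it is produced.** Let Z1 be the 1b test statistic and Z2 the statistic for the bilirubin difference, bivariate normal with correlation ρ and the same mean θ. The documents give neither ρ nor the relative effect sizes. The range ρ = 0.5 to 0.9 and the equal standardised effects are assumptions. Then

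E[Z2 given |Z1| > 1.96] = θ + ρ × [φ(1.96 − θ) − φ(1.96 + θ)] / power.

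At 80% power θ = 2.802 and the bracket divided by power is 0.350. With ρ = 0.5 the ratio is (2.802 + 0.175) / 2.802 = 1.06; with ρ = 0.9 it is (2.802 + 0.315) / 2.802 = 1.11.

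| Power | θ | ρ = 0.5 | ρ = 0.7 | ρ = 0.9 |
|---|---|---|---|---|
| 90% | 3.242 | 1.03 | 1.04 | 1.05 |
| 80% | 2.802 | 1.06 | 1.09 | 1.11 |
| 50% | 1.960 | 1.20 | 1.29 | 1.37 |
| 20% | 1.115 | 1.62 | 1.87 | 2.11 |

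**Coverage of the nominal 95% interval, given that it is produced** (simulation, 2 million draws per case): 96 to 97% at 80% power, 95% at 50%, and 87 to 92% at 20%. With no true effect, coverage is 81%, 67% and 41% for ρ = 0.5, 0.7 and 0.9. In that last case the average signed bias is zero, but the intervals that pass the condition miss too often.

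**With the condition removed**, the chance of no comparison is 0 and the selection ratio is 1.00. No sample size changes.

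**The case against.** The strongest reply is that little is lost. The 6-month primary outcome, itself a bilirubin threshold, is modelled unconditionally, and so is the 1b time to failure. A reader might infer that a null trial would leave the first-listed secondary outcome wholly unestimated. The documents do not support that. The condition is the 1b result, not the trial's overall result or the primary test, and those can disagree. The sentence speaks of profiles, whereas section 4.E lists concentration at named times. The closing sentence of section 5.B is unconditional and could be read to cover concentration as a continuous endpoint. This stands as far as it goes, but it does not settle the matter: bilirubin already has its own specific, conditional sentence under Aim 1, and a sentence about other endpoints most naturally means those not yet handled.

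A reader might also infer a conflict with section 6.C1, which expects that after a negative trial "the data may guide the medical community at large regarding the lack of efficacy of this approach". That passage does not mention bilirubin profiles, and it can rest on the primary outcome and on survival with native liver, neither of which is conditional. No contradiction follows.

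The condition could further be defended as a fixed testing sequence, with profiles tested only after 1b succeeds. The protocol declares no such purpose. Even if it did, this would justify withholding a claim of significance, not the estimate and its limits.

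Finally, inflation near the planned power is small and coverage there is at or slightly above nominal. That is correct. The larger figures need a true effect well below plan.

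**Conclusion.** The point holds in limited form. The protocol fixes a rule under which the only named between-arm comparison of bilirubin concentration over time, and its 95% limits, depend on a significant 1b result. Non-production is the main defect: about 95% under no effect and 20% at 80% power, which needs no assumption beyond the power of the 1b test. Inflation is secondary: about 3 to 11% between 90% and 80% power, under the assumed correlation of 0.5 to 0.9 and equal standardised effects. It would be wrong to describe this as a heavily biased result in the planned setting.

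The primary analysis, the sample size and the 1b hazard ratio are untouched. The change is worth making because a declared secondary outcome should not be estimated only when a related test succeeds.

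**What to change.** Replace the conditional sentence under Hypothesis 1b with, for example:

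*Whatever the result of the Cox model, bilirubin over time will be compared between arms, and the differences at 3 months after portoenterostomy and at 12 and 24 months of age will be given with 95% confidence limits, among infants alive with native liver, alongside the numbers transplanted or dead in each arm.*

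Also state that the 1b hazard ratio will be given with 95% limits in all cases.

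The clause on native liver is needed. In the survey in section 5.A2, 60 of 118 infants (51%) were transplanted by 24 months of age, and section 5.B counts transplant or death as failure in all analyses under Hypothesis 1a. An alternative consistent with that is to rank transplant or death as the worst outcome and compare ranks. One of the two should be chosen before unmasking.

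The cost is slightly more analysis output; the measurements are already scheduled. The drawback of the native-liver version is that it conditions on a post-randomisation event, so it should be labelled descriptive. The ranked version keeps all randomised infants, but its result is not a difference in mg/dL.

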the posttranslational carboxylation of glutamic acid to gamma-carboxyglutamyl residues in factors II (prothrombin), VII, IX, and X and proteins C and S. The major sign of vitamin K deficiency is coagulopathy. The dietary form of vitamin K is vitamin K₁ and as with the other fat soluble vitamins, vitamin K absorption requires the normal flow of bile into the intestinal lumen. Malabsorption of vitamin K in cholestasis as well as antibiotic use that impairs intestinal bacterial production (vitamin K₂), can lead to vitamin K deficiency. Vitamin K status is measured clinically by prothrombin time (PT) which is an index of vitamin K dependent clotting factors. Vitamin K deficiency is suggested when the PT is prolonged yet the partial thromboplastin time (PTT) is within normal range. A diagnosis of vitamin K malabsorption and deficiency is established when the prothrombin time normalizes after parenteral vitamin K supplementation. Subclinical vitamin K deficiency states have been identified by measuring serum undercarboxylated prothrombin (PIVKA-II). This protein is considered a sensitive functional indicator of vitamin K status⁷⁰. Since the liver synthesizes some coagulation factors, coagulopathies in cholestasis can be due to vitamin K deficiency, poor liver synthetic function, or a combination of both.

Toxic manifestations of vitamin K supplementation have not been observed⁵⁵.

4.N6. Fat-soluble Vitamin Supplementation

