Two central laboratories will be measuring vitamin levels for this study. A sample will be sent to the Pediatric CTSC Core Laboratory at The Children's Hospital in Denver which will perform all the tests except the PIVKA-II. The samples that are sent to Denver will be identified with the following personal health information: child's name, medical record number, and date of birth. The child's unique study code will not be shared. It is necessary for this information to be collected and shared because these are clinically indicated tests that will be reported to the site. These tests will be paid by the study.

PIVKA-II samples will be barcoded and sent to the NIDDK Repository . The NIDDK Repository will then batch ship these samples to Cincinnati Children's Hospital Medical Center for processing. The NIDDK Repository will verify which samples were sent to Cincinnati, and Cincinnati will send the results to the DCC. PIVKA-II is not being used clinically by the sites and these results will not be reported back to the site. These tests will be paid by the study.

Target vitamin levels:

- Vitamin A: A molar ratio of retinol:RBP will be used to assess vitamin A nutriture. A cut-off of 0.8 mol/mol will be used to define vitamin A deficiency. If a retinol:RBP ratio is below 0.8 and serum retinol is less than 20 ug/dl, the subject will be considered vitamin A deficient and supplementation will be recommended (see below). If the serum retinol is <20 ug/dl and the retinol:RBP ratio is >0.8, vitamin A status will be reassessed in one month. If the serum retinol is > 20 ug/dl and the ratio is < 0.8, vitamin A status will be reassessed in one month. If the serum retinol is greater than the upper limit of normal range, the vitamin A dose will be decreased by 50% and vitamin A status reassessed in one month.
- Vitamin D: The target serum 25-OH vitamin D concentration range is 15-45 ng/ml.
- Vitamin E: The target serum vitamin E:lipid ratio will be >0.6 mg/g in children less than 12 months of age and >0.8 mg/g in children older than 12 months of age. The upper limit of vitamin E:total lipids ratio will be 3.5 mg/g.
- Vitamin K: The INR will be used as surrogate marker of vitamin K status with a target INR<1.2

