Target vitamin concentration within normal range: When vitamin concentrations are within target range no changes will be made and vitamin levels will be retested at the 3 and 6 month follow-up visit and at 12, 18 and 24 months of age while a subject is receiving vitamin supplementation.

Target vitamin concentrations below normal range: When a vitamin result is below target range, supplementation of the specific vitamin(s) that is deficient will be prescribed and re-checked in one month (see Section 4.N9 for supplementation plan). If the vitamin level is within the target range there will be no further adjustments. When the vitamin level is still below target range, additional supplementation will be given as outlined below (Section 4.N9).

Target vitamin concentrations above normal range: When a subject is receiving the standard vitamin supplementation and one or more vitamin concentrations is above target range, the vitamin supplementation may be reduced to 1 ml per day and the vitamins that were within target range will be supplemented individually to have the same concentration as in the formulation of 2 ml of AquADEK®. All vitamins will be rechecked within one month and adjustments made as outlined in the protocol.

4.N10. Adjustment of Individual Vitamin Doses

When individual vitamins are found to be deficient, the vitamin will be prescribed, whenever possible, at the amount described below:

- Vitamin A: When a subject is vitamin A deficient, liquid vitamin A (intravenous preparation) may be given at 5000 IU by mouth with the AquADEK® each day and vitamin A status rechecked within one month. Doses orally of up to 25,000 – 50,000 IU vitamin A per day can be given for 1-4 weeks but will require weekly monitoring of vitamin status to prevent toxicity. Alternatively, when a subject is vitamin A deficient, 50,000 IU IM may be given once a month for two months. Vitamin A status is rechecked monthly with this regimen.

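### Hypothesis 4a cites a section without targets for vitamin sufficiency, and the 15-45 ng/ml range in 4.N9, read as written, scores over-replete infants as not vitamin D sufficient

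*Protocol*

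**What the plan says.** Section 5.B classifies each subject, vitamin by vitamin, as having achieved sufficiency or not, first with and then without supplementation. The definition is: "Vitamin sufficiency will be defined as having achieved the target concentration ranges specified in Section 4.N8". The outcome is modelled by logistic regression on bilirubin (continuous, or split at 1.5 mg/dL), with gender, race, major congenital anomalies and site. Hypothesis 4b uses the time to reaching target concentrations without supplementation.

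Section 4.N8 covers how vitamins are given. The targets are in 4.N9:

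- **Vitamin D:** "The target serum 25-OH vitamin D concentration range is 15-45 ng/ml".
- **Vitamin E:** lipid ratio above 0.6 mg/g under 12 months of age and above 0.8 mg/g over 12 months. A separate sentence adds: "The upper limit of vitamin E:total lipids ratio will be 3.5 mg/g".
- **Vitamin A:** a retinol:RBP deficiency cut-off of 0.8 mol/mol.
- **Vitamin K:** INR below 1.2, described as a surrogate marker.

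Section 4.N9 handles high values under their own heading, "Target vitamin concentrations above normal range", where supplementation may be reduced.

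On vitamin K, 4.N5 warns that "coagulopathies in cholestasis can be due to vitamin K deficiency, poor liver synthetic function, or a combination of both" and says of PIVKA-II: "This protein is considered a sensitive functional indicator of vitamin K status". Section 4.E lists INR both as the secondary vitamin K biomarker and as the first tertiary outcome, and lists PIVKA-II as tertiary. Section 5.A.3 expects a lower INR from better liver function.

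**The concern.** Hypothesis 4a holds that better bile drainage makes sufficiency more likely. A test of that needs an outcome that improves, or at least does not worsen, as an infant becomes more replete. A two-sided range lacks this property. Below 15 ng/ml and above 45 ng/ml are opposite states, and 4.N9 manages them in opposite directions, yet the binary outcome puts both into the not-achieved class. If better drainage raises 25-OH vitamin D, some infants leave the class at the bottom and others enter it at the top. The bilirubin coefficient then estimates a mixture of the two movements.

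The wrong section number adds to this: someone programming the outcome from 5.B finds no range in the section cited, and nothing in 5.B says how an above-range value is scored.

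Vitamin K raises a related question of interpretation. INR can change with synthetic function while vitamin K status stays the same, and the planned model has no term for synthetic function.

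**Working it through.** **No figure to reproduce.** Section 5.A2 says there are no data for power calculations on vitamin sufficiency, and the protocol gives no expected rate.

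**Step 1: which targets are two-sided.** From 4.N9, vitamin D clearly is. Vitamin E has one-sided targets plus a separate upper limit, so its status is ambiguous. Vitamins A and K each have one deficiency-side bound.

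**Step 2: is the vitamin D score monotone?** Suppose levels are normal with mean m and SD s (an assumption). With Φ the standard normal distribution function:

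- Rule as written: P(in range) = Φ((45 − m)/s) − Φ((15 − m)/s)
- Deficiency-side rule: P(≥15) = 1 − Φ((15 − m)/s)

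For fixed s the first is greatest at the midpoint, m = (15 + 45)/2 = 30 ng/ml, and falls beyond it. The second always rises with m. With s = 12 (assumed):

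| Mean, ng/ml | In 15-45 | At or above 15 | Above 45 |
|---|---|---|---|
| 25 | 75% | 80% | 5% |
| 30 | 79% | 89% | 11% |
| 35 | 75% | 95% | 20% |
| 40 | 64% | 98% | 34% |
| 45 | 49% | 99% | 50% |

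**Step 3: effect on a comparison by drainage.** The planned predictor is bilirubin, so the two groups below stand for poorer and better drainage, not for treatment arms. All means and SDs are assumed. The unadjusted odds ratio is [p₂/(1 − p₂)] / [p₁/(1 − p₁)], with p₂ for better drainage.

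| Poorer v better drainage, mean (SD) | At or above 15 | OR | In 15-45 | OR |
|---|---|---|---|---|
| 22 (10) v 30 (12) | 76% v 89% | 2.7 | 75% v 79% | 1.3 |
| 25 (12) v 35 (14) | 80% v 92% | 3.1 | 75% v 69% | 0.7 |
| 25 (12) v 40 (15) | 80% v 95% | 5.1 | 75% v 58% | 0.5 |

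Worked for the second row, better-drainage group: (45 − 35)/14 = 0.714 and (15 − 35)/14 = −1.429, so P(in range) = 0.762 − 0.077 = 0.686 (from unrounded values) and P(≥15) = 0.923.

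The first row shows dilution only: the difference falls from 14 to 4 points. The second and third rows reverse.

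**Step 4: a figure not used.** The only vitamin D comparison by jaundice status with a stated spread (4.N3: 48.9 ± 30.6 v 23.7 ± 9.5 ng/ml) is a rise after an oral tolerance test. It is not an on-supplement level and cannot size the effect here.

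**Step 5: vitamin K.** If 80% of infants are replete and a fraction f of those have INR of 1.2 or more from poor synthetic function alone (both assumed), the share scored sufficient is 0.80 × (1 − f): 76%, 72%, 64% and 56% for f = 5%, 10%, 20% and 30%. Scored sufficiency changes while vitamin K status does not.

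**The case against.** - **The word achieved may mean reached the lower bound.** The mainly one-sided targets for A, E and K support that reading. But no passage says so, and the reference is to ranges. The ambiguity itself needs settling.
- **Doses are not fixed.** Above-target infants may be cut to 1 ml/day and are rechecked within a month (4.N9), and AquADEK may be stopped once bilirubin is below 1.5 mg/dL (4.M4). An infant who overshoots and returns to range might later count as having achieved sufficiency. This stands: it limits the effect by an unknown amount, and the single-draw calculation above does not model it.
- **The inputs are assumed, and deficiency may dominate.** Section 4.N3 reports 25-OH vitamin D deficiency in 5 of 6 infants with poor bile flow after portoenterostomy. If few infants exceed 45 ng/ml, little changes. This also stands.
- **The level is reported anyway.** Section 4.E lists serum 25-OH vitamin D as a secondary measure, so higher levels would be visible there. That helps a reader but does not repair the binary outcome of 4a.
- **INR is openly a surrogate.** The protocol states its limitation and collects PIVKA-II. It gives PIVKA-II no cut-off and calls it sensitive, not specific. A reader might infer that INR should be replaced; the documents do not support that, since a swap would remove the threshold the binary outcome needs.

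A reader might also infer that the sufficiency rule as a whole misclassifies infants, or that a steroid benefit would appear as harm. Neither follows: only vitamin D is clearly two-sided, the model uses bilirubin and not treatment arm, and the reversal depends on the means chosen.

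**Conclusion.** The definition needs correcting. Its cross-reference is wrong and, read as written, it counts vitamin D excess as insufficiency, so the vitamin D outcome is not monotone in repletion. The same could apply to vitamin E if the 3.5 mg/g limit is taken as part of the target. In the assumed examples the consequence runs from dilution (odds ratio 2.7 to 1.3) to reversal (3.1 to 0.7, or 5.1 to 0.5). These rest on normal levels, the chosen means and SDs, one measurement per infant and no dose adjustment, so they show what is possible and do not estimate what will occur.

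For vitamin K, INR may remain the stated surrogate, but an INR difference alone should not be read as a vitamin K effect. Only secondary Aim 4 is affected; the primary endpoint is not.

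**What to change.** Before unmasking, and for outcome scoring only:

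1. In 5.B, Hypothesis 4a, point the definition to 4.N9.
2. Define sufficiency by the deficiency-side bound of each 4.N9 target: 25-OH vitamin D at least 15 ng/ml; vitamin E:lipid above 0.6 or 0.8 mg/g by age; retinol:RBP by the 0.8 mol/mol cut-off; INR below 1.2. Use the same bounds for target concentrations in Hypothesis 4b.
3. Report values above 45 ng/ml (vitamin D) and above 3.5 mg/g (vitamin E) separately as excess.
4. Keep INR as secondary item 4d in 4.E. Add PIVKA-II, analysed as a continuous value, as a supportive analysis beside it, with a sentence that INR alone does not establish a vitamin K effect.

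The clinical dosing ranges and adjustment rules are untouched. The cost is a few lines in 5.B and one supportive table; the samples are already scheduled. No PIVKA-II cut-off is needed if it is analysed as continuous.
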